We expect to enroll between 30-50 patients based on eligibility over 2.5 years of recruitment. This estimate is based on the most recent hospital admissions data since the start of the COVID-19 pandemic estimating approximately 100 patients will qualify for the study over 2.5 years. Participants will be randomized 1:1 to receive the intervention. Recruitment and retention will be assessed during the trial as outcomes.

b. Inclusion and Exclusion Criteria

Children \geq 6 years and <19 years of age admitted with TBI (defined as injury to the head from external forces with severity mild, moderate, or severe classified by Glasgow Coma Scale) will be included.

Children under the age of 6 years will be excluded due to increased variability in baseline sleep patterns, daytime napping, and lack of standardized tools identifying sleep outcomes between children younger and older than 6 years. Patients over age 18 years will be excluded as they are primarily treated in adult care units and the study focus is pediatric. Patients unable to tolerate enteral medications within 72 hours of hospital admission, as defined by the clinical care Attending Physician, will be excluded from the study. Patients undergoing dialysis, requiring extracorporeal life support, or with significant liver dysfunction (defined as aspartate aminotransferase (AST) or alanine aminotransferase (ALT) more than 2 times the upper limit of normal for age) will be excluded. Patients about whom the Attending Physician has any safety

concerns regarding use of melatonin as per clinical judgement will be excluded from the study. Patients with abusive trauma will be excluded. Suspected or known prisoners are excluded. Pregnant patients are excluded. There will be no requirement for contraception during the trial in female patients of child-bearing age. Patients must have a parent or guardian with whom they reside in order to participate in the study given the parent-reported measures used for outcomes.

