- Children younger than 7 years: Assent is not required because the subjects are so young they cannot reasonably be consulted. However, a simple verbal explanation of the study procedures should be given if appropriate.

- Children ages 7 – 14 years: Researchers may obtain assent verbally and document this on the consent form or elsewhere in the research record, or researchers may ask the subject to sign an assent form after discussing the study with the subject at a level appropriate to the subject’s understanding. Researchers will use the OHSU assent template.
- Children ages 15 – 17 years: The subject may sign the consent form along with his or her parent(s) or guardian as documentation of assent. A separate assent form is not needed.

For non-English speaking participants, we have 24/7 available translators over the phone that will assist with the consent process. We will submit short consent form(s) for IRB review and approval as appropriate. An interpreter will assist with the initial consent process and subsequent study visits for all non-English speaking subjects.

Other than screening procedures described above, no modifications to the written consent process will be used.

6. Procedures Involved

Data Collection: Patients meeting inclusion criteria (see Eligibility Criteria) will be approached within 72hours of hospital admission to provide written consent and assent where appropriate. Parents will be asked to complete “baseline” assessments retrospectively to reflect the patient’s pre-injury status at the time of consent. Additional information will be collected by the study team from parents via survey and medical record review for demographic and clinical variables. Our goal recruitment and completion is for 30-50 patients.

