	
adherent if device worn for ≥5 nights consecutively; we will assess sleep routines through actigraphy; will be counted as unknown if did not participate in the actigraphy portion
 
Quantitative survey: "How many nights each week did you take the study medication since discharge?"
 
None, 1-3, 3-4, 5-7, All
 
Quantitative survey response: "Did you receive sleep education with your hospital discharge paperwork?"; choices of a) did not receive discharge paperwork; b) I did not receive any sleep education at discharge; c) I received it, but did not use it; d) I received it, but did not find it helpful; e) I received it, and found it helpful; responses to this question will also be compared with the discharge instructions within the electronic health record to determine if the resource was provided as intended.
	Descriptive percent; Chi-square to compare intervention arms
Acceptability Outcomes		
*Adverse Events (discharge, 30-day)	
Qualitative response to survey: "Did you have any new medical problems since the last study visit?"
 
Quantitative yes/no response: "Did you have any of the following symptoms since the last visit"
 
 a. Nausea b. Vomiting c. Diarrhea d. Drowsiness e. Fatigue f. Headache g. Behavioral changes h. Vivid dreams i. Nightmares j. Waking up at night k. Itchy skin l. Rash m. Appetite changes n. Bodily pain or aches o. Chest pain p. Enuresis or bedwetting q. Dizziness r. Tinnitus or ringing in the ears s. Feeling cold 
Evaluation of medical record, patient assessments to quantify adverse events and unexpected problems collected as a dichotomized yes/no and number of events
	
Thematic analysis
 
Descriptive percent and mean with standard deviation; Chi-square (yes/no) and Mann-Whitney U test (continuous) to compare intervention arms

Satisfaction (30-day)	Quantitative rankings on a likert scale survey: experiences with the study overall, consent process, study team, study intervention, questionnaires, Actigraphy devices, care received	Descriptive median and interquartile range; Mann-Whitney U tests

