a. Sharing of Results with Subjects

Data from this clinical trial will not be shared directly with participants. The results of the clinical trial and de-identified data will be made in accordance with NIH regulations and clinicaltrials.gov.

b. Data and Specimen Banking

No specimens will be stored. Study records will be retained for the longest regulatory retention period. After that time, records will be destroyed in a confidential manner.

8. Data Analysis

See Table 1 for outline of data analysis planned for study outcomes. As this is a pilot intervention trial, the focus will be on feasibility and acceptability of the pragmatic intervention trial. We will also explore effectiveness outcomes, but recognized we will be underpowered for a definitive effectiveness trial within this heterogeneous population selected to be representative of the population of interest. We will use our pilot trial to inform a future larger trial that will include longitudinal real world health outcomes relevant to the pediatric TBI population if supported by our preliminary results.

Prior to evaluating outcomes, we will perform a thorough descriptive analysis of participant baseline characteristics (age, race, ethnicity, gender, pre-injury comorbidities, TBI characteristics including severity, location, and type). We will examine patterns of missingness in our outcomes collected at 1-month, differences in participant and non-participant characteristics, and differences in participants who completed versus dropped out of the study to ascertain potential bias. Additionally, we will describe and compare the distribution of patient and clinical characteristics, including age and TBI severity, across treatment groups to ensure our randomization protocol was successful. Comparisons between groups will be made using chi-square tests for categorical variables. Depending on characteristics of the data, t-tests and Mann-Whitney U tests will be used to compare continuous variables between groups. We plan to perform both intention to treat and per protocol analyses.

Quantitative feasibility outcomes will be presented as a percentage of patients, the denominators of which are listed in Table 1. Comparisons between groups will be made with chi-square tests.

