Quantitative acceptability outcomes for adverse events will be dichotomized to yes/no and evaluated as a total number for each patient summarized using percent and median with interquartile range (IQR), respectively. Acceptability outcomes for satisfaction will be measured using Likert scales for which we will present results as medians and IQR. Chi-square tests will be used to compare dichotomized outcomes between treatment groups, and Mann-Whitney U tests will be used to compare total number of events. Effectiveness outcomes will be summarized using means and standard deviations, except for daytime sleep episodes which will be summarized as a median and IQR; these outcomes will be summarized for the overall study population and by treatment group. We will primarily examine the effectiveness of our intervention using linear regression to assess differences in the total SDSC score across treatment groups at 1-month. Linear regression will allow us to assess differences in effectiveness outcomes while controlling for covariates that may confound this relationship; covariates of particular interest will include age and TBI characteristics. Covariates identified in our initial descriptive analysis as significantly different between treatment groups, and covariates significantly associated with SDSC total score in bivariate analyses will also be explored with multiple linear regression.

Secondary effectiveness outcomes that specifically evaluate sleep phenotypes (measured by questionnaire and actigraphy) will be similarly evaluated with linear regression, except daytime sleep episodes which will be modeled using a count model, such as Poisson or negative binomial regression. For these secondary effectiveness outcomes, our focus is the magnitude of the association rather than statistical significance, as multiple comparisons will be made. Our primary goal with this secondary analysis will be to determine if the intervention appears effective for particular phenotypes that could be targeted in future studies. Results of these secondary analyses will be used as estimates for effect sizes in future intervention study design.

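### One ordered adherence item (nights per week) is compared with an unordered chi-square; a rank or trend test would suit it better, at almost no cost

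*Combined protocol and SAP*

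**What the plan says.** Table 1 lists several adherence measures under Feasibility Outcomes. One is a survey question, "How many nights each week did you take the study medication since discharge", with the options "None, 1-3, 3-4, 5-7, All". The analysis given in the adherence row is "Descriptive percent; Chi-square to compare intervention arms". Section 8 repeats this for all quantitative feasibility outcomes: "Comparisons between groups will be made with chi-square tests". Neither place names a trend version, category scores, an exact version or a rule for collapsing this item.

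The satisfaction items, also ordered, are treated differently. Table 1 gives "Descriptive median and interquartile range; Mann-Whitney U tests", and section 8 states: "Acceptability outcomes for satisfaction will be measured using Likert scales for which we will present results as medians and IQR".

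On size, section 6 says "Our goal recruitment and completion is for 30-50 patients", and section 5a says "Participants will be randomized 1:1 to receive the intervention". Adherence has no asterisk in Table 1, so it is not marked as a primary outcome. It is also measured by pill count, as a yes/no outcome with a 75% threshold. The plan states no alpha, effect size or power for the nights-per-week item.

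**The concern.** The five answers run from no nights to every night. A Pearson chi-square on the full table treats them as five unrelated labels and spreads its sensitivity over four degrees of freedom. If children in one arm simply take the product less often, that drift is what a rank or trend test is built to detect and what the chi-square dilutes. With 15 to 25 per arm, many expected counts also fall below 5, so the asymptotic reference distribution is unreliable. The plan gives no reason for treating two sets of ordered survey items in one table differently.

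At stake is a modest matter: a real difference between arms in product use could be reported as no evidence of a difference, in a pilot meant to inform a larger trial.

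**Working it through.** The plan has no figure to reproduce for this item, so the check compares the power of the two tests by simulation.

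**Inputs from the documents.** Five ordered levels. A total of 30–50 at 1:1 gives 30/2 = 15 to 50/2 = 25 per arm. If 30–50 is the number enrolled and retention just meets its goal (above 90%), about 13 to 22 per arm have 30-day data (15 × 0.9 = 13.5; 25 × 0.9 = 22.5).

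**Assumptions, not in the documents.** Two-sided alpha of 5%; all five levels kept; a one-directional proportional-odds shift; reference-arm distribution 5/10/15/30/40% from None to All, with others tried below.

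**The shift.** Each cumulative odds is multiplied by the odds ratio (OR). The reference cumulative proportions 0.05, 0.15, 0.30, 0.60 have odds 0.053, 0.176, 0.429, 1.5. At OR 3 these become 0.158, 0.529, 1.286, 4.5, or cumulative proportions 0.136, 0.346, 0.563, 0.818. The shifted arm is therefore about 14/21/22/26/18%.

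**Sparse cells.** With no difference and 20 per arm, expected counts in each arm are 20 × (0.05, 0.10, 0.15, 0.30, 0.40) = 1, 2, 3, 6, 8, so 6 of 10 cells are below 5. In simulated tables at 15–25 per arm the share is about 55–74% of non-empty cells.

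**Power**, 20,000 simulated trials per setting, Pearson chi-square (empty columns dropped) against tie-corrected Mann-Whitney. Relative loss = 1 − (chi-square power / Mann-Whitney power).

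| Per arm | OR | Chi-square | Mann-Whitney | Relative loss |
|---|---|---|---|---|
| 15 | 3 | 18% | 36% | 1 − 18/36 = 50% |
| 20 | 3 | 26% | 47% | 1 − 26/47 = 45% |
| 25 | 3 | 33% | 55% | 1 − 33/55 = 40% |
| 15 | 4 | 29% | 53% | 1 − 29/53 = 45% |
| 20 | 4 | 42% | 66% | 1 − 42/66 = 36% |
| 25 | 4 | 52% | 76% | 1 − 52/76 = 32% |

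Repeat runs agree within about 4 points; at 20 per arm and OR 3, chi-square ranges over 24–27%. Under no difference, chi-square rejects about 3–5% and Mann-Whitney about 4–5%, so neither test is inflated.

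**Other reference distributions.** High adherence (5/5/10/30/50%), OR 2: 7.7% against 16.9% at 15 per arm (54% lost) and 12.8% against 25.5% at 25 per arm (50% lost). Ceiling (3/3/4/20/70%), OR 2, 15 per arm: 6.0% against 15.2% (1 − 6.0/15.2 = 61% lost).

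**How much is due to order alone.** In large samples a proportional-odds shift gives both tests about the same noncentrality, on 4 degrees of freedom for chi-square and 1 for the rank test; the relative loss then peaks at about 41%. Permutation versions of both tests remove the sparse-cell distortion and give losses of about 21–43%. For the high-adherence distribution, 15 per arm, OR 3, the permutation versions give 21.4% against 35.6% (1 − 21.4/35.6 = 40% lost) and the asymptotic versions 17.6% against 36.9% (1 − 17.6/36.9 = 52% lost).

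**Two cases that go the other way.** If answers polarise rather than shift, at 25 per arm chi-square has 87% power and Mann-Whitney 7%. If the item is collapsed to the top two levels against the rest (5/10/15/30/40% reference, OR 3), chi-square against Mann-Whitney is 31% vs 36%, 38% vs 47% and 52% vs 56% at 15, 20 and 25 per arm, a loss of about 14%, 19% and 7%.

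**The case against.** The strongest reply is that little depends on this test. The item is an unasterisked companion to the pill count, for which a chi-square is standard. Percentages are the first analysis listed, and no benchmark or decision rule uses the between-arm comparison. Section 6 does name utilization among the acceptability measures, but ties it to no test of this item. All of this stands, and it sets the severity.

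A second reply is that the loss is conditional. The alpha, odds ratios and reference distributions are assumed, a one-directional shift favours a rank test, and the plan does not say that five levels are kept. This also stands. Against collapsing, the plan states its cut where it wants a yes/no outcome (pill count, device wear, adverse events) and states none here.

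A reader might infer three stronger things that the documents and figures do not support:

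- That ignoring order by itself discards half the power. At most about 40% comes from that; the rest is the sparse asymptotic test.
- That the plan throws away a signal the pilot would otherwise detect. At odds ratios 2–3 with the 5/10/15/30/40% reference, Mann-Whitney itself reaches only about 16–57%.
- That chi-square is wrong for feasibility outcomes in general. Several are binary, and there the choice is sound.

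Finally, the answer options overlap: 3 falls in two of them, and 5-7 includes every night. This blurs any ranking, so changing the test alone is an incomplete remedy.

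**Conclusion.** The mismatch is real and confined to one item: ordered answers are given an unordered test, while the plan's satisfaction items get a rank test. If the five levels are kept and the difference runs in one direction, then at 15–25 per arm, two-sided 5% and odds ratios 2–4, the asymptotic chi-square has roughly 30–60% less power than Mann-Whitney. Only the sample size and the response scale come from the documents. The error is one of reduced sensitivity, not of false positives, and it does not touch a primary outcome. This is a low-severity improvement.

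**What to change.** In Table 1 (Adherence) and section 8, for the nights-per-week item only, replace chi-square with Mann-Whitney U or a test for trend, in an exact or permutation version because of the sparse cells. Keep the percentages in each category by arm as the main summary. Leave chi-square in place for the binary and unordered items.

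Make the response options non-overlapping, so that three nights and seven nights each have one possible answer. If answers have already been collected on the present scale, keep those categories and state the order in which they will be ranked.

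The cost is a few words in the plan and a small survey edit, with no new data. The price is lower power against non-monotone differences such as polarised use, which the category percentages would still show.

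### The primary adverse-event outcome is summarised only as a yes/no and a per-patient total; both dilute an excess in a single symptom, and the yes/no may be near ceiling.

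*Combined protocol and SAP*

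**What the plan says.** Table 1 (Section 6) marks adverse events as a primary acceptability outcome, collected at discharge and at 30 days. It has three sources:

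- an open question on new medical problems, analysed thematically;
- a checklist of 19 items (a to s) asking "Did you have any of the following symptoms since the last visit", each answered yes or no;
- a review of the medical record and patient assessments, with events "collected as a dichotomized yes/no and number of events".

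The checklist has no stated rule for new onset, worsening, severity or relatedness, and no baseline collection is listed. One item is "Waking up at night"; drowsiness and fatigue are also on the list.

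Section 8 sets the quantitative analysis: "Quantitative acceptability outcomes for adverse events will be dichotomized to yes/no and evaluated as a total number for each patient". It adds that "Chi-square tests will be used to compare dichotomized outcomes between treatment groups" and that "Mann-Whitney U tests will be used to compare total number of events". Table 1 summarises the count by mean and standard deviation; Section 8 uses median and interquartile range. Neither place says whether the yes/no is one answer per patient or one per symptom.

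**The concern.** Pooling 19 items into one yes/no or one total suits a treatment that shifts many symptoms together. It suits poorly a treatment whose unwanted effects may be one or two specific symptoms. Section 11 lists such symptoms for melatonin, vivid dreams and drowsiness among them, and says that placebo studies report similar ones, so some background in both arms is to be expected.

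The total also has mixed direction. Waking at night, drowsiness and fatigue overlap effectiveness outcomes in Table 1: wake after sleep onset and daytime sleep by actigraphy, and the PedsQL fatigue scale. A better-sleeping child scores lower on the harm total, which can offset a rise elsewhere.

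The pilot is meant to inform a larger trial. A null result on these two summaries could be read as good tolerability when a specific excess had little chance of showing.

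**Working it through.** The plan states no symptom rate, effect size, alpha or power for this outcome, so there is no figure to reproduce.

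**Inputs from the documents.** 19 items (Table 1). "We expect to enroll between 30-50 patients" (Section 5a), allocated 1:1, so 15-25 per arm. Chi-square for the yes/no and Mann-Whitney for the total (Section 8).

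**Assumptions.** Background rate p of 5%, 10% or 20% for every symptom; two-sided alpha 0.05; melatonin raises one symptom by 40 points and leaves the other 18 alone; symptoms independent unless stated.

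**Step 1: any-symptom rate.** Control: 1-(1-p)^19. Melatonin: 1-(1-p)^18 × (1-p-0.40).

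| p | Control | Melatonin | Difference |
|---|---|---|---|
| 5% | 1-0.377 = 62% | 1-0.397×0.55 = 78% | 16 points |
| 10% | 1-0.135 = 86% | 1-0.150×0.50 = 92% | 6 points |
| 20% | 1-0.014 = 99% | 1-0.018×0.40 = 99% | 1 point |

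A 40-point excess in one symptom thus shrinks to between 16 points and 1 point.

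**Step 2: sensitivity of the ceiling.** With correlated symptoms (beta-binomial, intra-class correlation 0.2), the control rates fall to 31%, 53% and 79%. With independent symptoms at only 1% each, the rate is 17%.

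**Step 3: power for the one-symptom excess.** The yes/no and single-symptom figures are exact enumerations of the uncorrected Pearson chi-square. The total is Mann-Whitney on 20,000 simulated trials per cell. Ranges run from 15 to 25 per arm.

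| p | Any-symptom yes/no | Total | That symptom alone |
|---|---|---|---|
| 5% | 17-24% | 18-29% | 79-96% |
| 10% | 5-10% | 12-18% | 73-91% |
| 20% | 0% | 8-12% | 63-87% |

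Simulation runs of the total differ by a point or two at the ends (another gave 7-27% overall). The total is weak because its mean rises by 0.40 against a control standard deviation of √(19p(1-p)), which is 0.95, 1.31 and 1.74. The shift is therefore 0.42, 0.31 and 0.23 standard deviations.

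**Step 4: offsetting.** Set night waking to 52% under placebo, borrowing the sleep-disturbance rate in Section 3 (not a rate for this item). If melatonin lowers it by 20 points while another symptom rises by 40, power for the total is 6-10%. If it falls by 40 points, power is 4-5%, about the false-positive rate.

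**Step 5: a broad rise.** If all 19 symptoms go from 20% to 40%, Mann-Whitney power is 67-100% (intra-class correlation 0 to 0.2, both sample sizes), against 0-51% for the yes/no. For 20% to 30% with correlation 0.1, Mann-Whitney power is 35% at 15 per arm and 56% at 25.

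**The case against.** A reader might infer that the outcome sits at ceiling and cannot show any melatonin effect. The documents do not support that. They give no symptom rates; clustering lowers the any-symptom rate, and 62% or 31% is not a ceiling. The same Section 8 sentence that sets the yes/no also sets the per-patient total, which Step 5 shows can detect a large, broad increase.

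The per-patient reading can also be contested. Table 1 heads the checklist as a yes/no response item by item, and the phrase about a dichotomised result and a number of events belongs to the medical-record entry. Each symptom might therefore already be intended for a percentage and a chi-square by arm. This stands as an ambiguity. Section 8, however, pairs the yes/no with a total for each patient, so one answer per patient is the more natural reading. If per-symptom reporting is intended, the plan should say so.

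The single-symptom powers flatter the alternative: they assume a 40-point rise in one symptom known in advance, with no multiplicity adjustment. Bonferroni over 19 symptoms reduces them to 19-67%; an unadjusted 20-point rise gives 23-56%. This stands, and is why the per-symptom table should be descriptive.

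Finally, this is a pilot with no power target, and harms are also captured by the open question, chart review and DSMB review of serious events by arm. That limits the consequence, but those routes do not replace a tabulation of the checklist.

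**Conclusion.** The concern holds in a limited form. As most naturally read, the plan reduces a primary outcome to two summaries, and each dilutes an excess confined to one symptom: about 0-24% power for the yes/no and about 8-29% for the total, under the assumed 40-point rise, independent symptoms, background rates of 5-20% and 15-25 per arm. The any-symptom yes/no may be near ceiling, but how near depends on rates and clustering that the documents do not give (62-99% if independent, about 31-79% at intra-class correlation 0.2). The total keeps information about a broad rise, but it mixes possible harms with items on which the intervention may help. The undefined yes/no and the mean/SD against median/IQR conflict stand without any assumption. The plan should be changed, but data collection is not compromised: each item is recorded separately, so the remedy lies in the analysis.

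**What to change.** In Table 1 and Section 8:

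- State that each checklist symptom is reported as a percentage by arm with a risk difference and 95% CI, descriptively and without a multiplicity claim. Intervals will be wide: at 20% in both arms the approximate half-width is 1.96×√(2×0.2×0.8/n), or 29 points at n = 15 and 22 points at n = 25.
- Keep the per-patient count as a supporting summary. Show it also without waking at night, drowsiness and fatigue, while still reporting those three as symptoms; Section 11 lists drowsiness among the symptoms reported with melatonin, so it must not disappear.
- Define the any-event yes/no: whether it covers the checklist, chart-recorded events or both, and whether it is per patient.
- Use one summary for the count in both places.

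The cost is a change of wording and a longer table from data already planned. The downside is many rows and no single p-value. Rewording the checklist question to ask about new or worse symptoms would help interpretation, but is optional: it changes the instrument, not just the analysis, and would apply only to children not yet assessed.

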No serious adverse events were reported in recent meta-analyses of studies using melatonin conducted in children with neurodevelopmental disorders, including epilepsy, or in a recent adult trial comparing melatonin and placebo, but melatonin appeared to effectively improve sleep. No serious adverse events were reported in a recent randomized trial in pediatric concussion using doses up to 10mg (double this trial's maximum dosing).[76] The potential benefit of improved sleep after TBI in our study compared to the risk associated with melatonin is likely as favorable to standard care given >50% have disturbed sleep after discharge without treatment and SWD are associated with worse cognitive functions and quality of life in pediatric TBI patients.

Given the ubiquitous use of melatonin in pediatric clinical care and research studies in a variety of pediatric populations with medical, developmental, and psychiatric disorders, no patients will be excluded for underlying medical conditions or concomitant medication use, outside of exclusion criteria above. Patients will be excluded from the trial if the clinical care Attending Physician deems the patient unable to tolerate enteral medications or otherwise has safety concerns regarding use of melatonin.

There will be no requirement for use of contraception in female participants of child-bearing age given no known adverse effects of melatonin in pregnancy and short duration of the intervention. Pregnant patients will be excluded from the trial or withdrawn immediately from the trial if become pregnant.

The educational intervention proposed in this study is of minimal risk given it is a handout with resources to promote healthy sleep. As part of our acceptability outcomes, we will evaluate utilization and usefulness of this portion of the intervention.

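### The primary adverse-event outcome is summarised as a yes/no and a per-patient total, with no comparison by symptom, so a rise in one specific melatonin-associated symptom is unlikely to show.

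*Combined protocol and SAP*

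**What the plan says.** Table 1 (section 6) stars adverse events as a primary acceptability outcome, collected at discharge and at 30 days. One component is a prompted checklist, "Did you have any of the following symptoms since the last visit", with 19 items running from a to "s. Feeling cold". Another is a review of the medical record and patient assessments, "collected as a dichotomized yes/no and number of events".

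Section 8 gives the analysis rule: "Quantitative acceptability outcomes for adverse events will be dichotomized to yes/no and evaluated as a total number for each patient". The tests follow: "Chi-square tests will be used to compare dichotomized outcomes between treatment groups, and Mann-Whitney U tests will be used to compare total number of events". Neither place names a percentage or a comparison for each symptom.

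Section 11a (Risks to Subjects) lists the symptoms reported in melatonin studies: itchy skin, rash, stomach upset, appetite changes, emesis, drowsiness, blurred vision, vivid dreams and bodily pain. It adds that placebo studies report similar symptoms. The protocol gives no expected rate for any checklist item, and no significance level or target effect for adverse events.

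**The concern.** The acceptability question is largely about particular symptoms. The checklist places them beside complaints that may come from the injury itself, such as "d. Drowsiness e. Fatigue f. Headache g. Behavioral changes", dizziness and waking at night. That overlap is a clinical assumption, but a plausible one in children hospitalised with head injury.

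If the 19 answers become one yes/no per child, a child who already has any one complaint cannot show an added one. If they become a total, one extra symptom is a small shift against the spread of the other 18. Either way, a clear excess of drowsiness or vivid dreams could sit in the data while both planned comparisons look similar between arms. The pilot is meant to inform a larger trial, and these summaries would not tell its designers which symptom to watch.

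**Working it through.** The plan states no figure for this outcome, so there is none to reproduce. The check asks how far each planned summary moves when one symptom triples on melatonin.

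**Inputs from the documents.** 19 items (Table 1); 30–50 children randomised 1:1, so 15–25 per arm before dropout (section 5a).

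**Assumptions.** Two-sided 0.05; equal placebo rate p for all items, at 5%, 10% or 20%; one item rises to 3p; symptoms within a child are independent or share a latent factor with correlation 0.3 to 0.6.

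**Step 1: any-symptom rate under independence.** Placebo: 1 − (1 − p)^19. Melatonin: 1 − (1 − p)^18 × (1 − 3p).

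- p = 5%: 1 − 0.95^19 = 62.3%; 1 − 0.95^18 × 0.85 = 66.2%.
- p = 10%: 1 − 0.90^19 = 86.5%; 1 − 0.90^18 × 0.70 = 89.5%.
- p = 20%: 1 − 0.80^19 = 98.6%; 1 − 0.80^18 × 0.40 = 99.3%.

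The shift is at most about 4 points, even at 5%, where there is no ceiling. Dilution is therefore the general cause, and a high background rate adds to it.

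**Step 2: the total.** At p = 10% the mean goes from 19 × 0.10 = 1.9 to 18 × 0.10 + 0.30 = 2.1. The simulated standard deviation is 1.3 to 3.4, depending on correlation.

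**Step 3: power by simulation.** 1,000 trials per setting, correlations 0, 0.3 and 0.6; power ranges run over the correlations.

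| One item | Placebo any-symptom rate (correlation 0 / 0.3 / 0.6) | Yes/no chi-square, 15–25 per arm | Total, Mann-Whitney, 15–25 per arm | Item alone, 15 per arm | Item alone, 25 per arm |
|---|---|---|---|---|---|
| 5% to 15% | 62 / 44 / 28% | 4–7% | 3–6% | 8–10% | 20–22% |
| 10% to 30% | 87 / 64 / 44% | 4–8% | 5–8% | 26–27% | 43–47% |
| 20% to 60% | 99 / 84 / 65% | 0–11% | 5–11% | 62–63% | 85–88% |

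A second simulation, with correlations 0, 0.3 and 0.5, gave about 0–8% for the yes/no and 4–13% for the total. For the item it gave 8–21%, 28–45% and 62–87%. Differences of a point or two between the runs are simulation error.

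**Step 4: several symptoms rising together.** Assumed placebo rates: four items at 50%, drowsiness at 20%, the other 14 at 10%. Drowsiness triples to 60% and seven of the 10% items triple to 30%. The Mann-Whitney test on the total then has power 76%, 27% and 20% at 15 per arm, and 95%, 47% and 33% at 25 per arm (correlations 0, 0.3, 0.5). A chi-square on one 10%-to-30% item has 26–30% and 43–47%.

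**Step 5: what an item-level estimate would look like.** Half-width of a 95% interval for a risk difference: 1.96 × √[(p₀(1 − p₀) + p₁(1 − p₁))/n].

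- 20% against 60%: 1.96 × √(0.40/15) = 32 points; 1.96 × √(0.40/25) = 25 points.
- 10% against 30%: 1.96 × √(0.30/15) = 28 points; 1.96 × √(0.30/25) = 21 points.

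**The case against.** **The collapse is not spelled out.** Section 8 attaches the per-patient wording to the total, and Table 1's yes/no-and-count phrase belongs to the medical-record entry. Item-by-item percentages would be compatible with the text. This stands as a caution. But answers that are already yes/no need no dichotomising, so one yes/no per child is the more natural reading. If a by-symptom analysis was meant, saying so costs a sentence.

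**Saturation is assumed.** A reader might infer that nearly every child will be a yes in both arms. The documents do not support that, because they give no symptom rates. The nearest figure, ">50% have disturbed sleep after discharge without treatment" in section 11a, is a general sleep-disturbance rate and not a rate for any checklist item. At 5% per item the any-symptom rate is only about 33–62% at correlations up to 0.5.

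**The total is not useless.** A reader might also infer that the plan would report similar adverse events almost whatever melatonin does. Step 4 contradicts this: the total has 20–95% power when eight symptoms triple, and often matches or beats a single item.

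**Item-level tests are weak too.** This is true for uncommon symptoms. Nineteen independent tests at 0.05 would also give a false positive in 1 − 0.95^19 = 62% of trials. This argues for estimates with intervals instead of tests.

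**It is a pilot with other safety information.** There is an open question on new medical problems, medical-record review, and reporting of serious adverse events by arm to the monitoring board (section 10). A separate monitoring plan exists that is not among these documents. Low power alone is no fault in 30–50 children. But thematic analysis gives no rates by arm, and the board's described review centres on serious events and deaths. For secondary sleep outcomes, section 8 already prefers magnitude to significance so as to find responsive phenotypes. The same reasoning fits here.

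**Conclusion.** The point holds as a gap in a primary outcome's analysis: no by-symptom comparison is named, and neither named summary can be relied on to show a rise in one specific symptom. Over the assumed rates and correlations, a tripling of one item moves the any-symptom rate by no more than about 9 points, and neither planned test detects it in more than about one trial in seven. The item itself is more responsive, clearly so at 10% or above and only modestly at 5%. The result rests on reading the yes/no as one per child, on assumed symptom rates, and on a single-symptom effect. It does not show that the yes/no will be saturated or that the total is a poor measure of overall burden. The change is a cheap improvement and should be made.

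**What to change.** In section 8 and the adverse-event row of Table 1:

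- Keep the yes/no and the total, and state whether the yes/no is one per child.
- Add a by-symptom table: for each of the 19 items, the percent by arm and the risk difference with its 95% confidence interval.
- Name in advance, as the focus, the checklist items that match section 11a: drowsiness, vivid dreams, itchy skin, rash, nausea, vomiting, appetite changes and bodily pain. Blurred vision is in section 11a but has no checklist item.
- Label the table as descriptive and without multiplicity control.

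The same edit can settle how the count is summarised: Table 1 says mean with standard deviation, section 8 says median with interquartile range.

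The cost is wording only, since every item is already collected. The downside is 19 more estimates with wide intervals, which must not be read as tests. There is no need to demote the total or to change the source of the patient-level yes/no.
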